7.1. Primary Efficacy Endpoints

The primary efficacy endpoints are the safety and tolerability of the combination and ORR within each tumor-specific cohort.

7.2. Secondary Efficacy Endpoints

The secondary efficacy endpoints are TTR, time to next treatment and DOR.

7.3. Exploratory Endpoints

The exploratory endpoints are WT1-specific immune response dynamics in PB, select general immunodynamics assessments (in PB and tissue samples, as applicable), genomic testing (including MSS/MSI assessment for CRC) in tissue samples, as well as OS, and PFS.

7.4. Sample Size Calculations

Approximately 90 patients will be enrolled in the study. The planned number of patients within each tumor-specific cohort is as follows: CRC (N = 20), OvC (N = 20), SCLC (N = 20), TNBC (N = 15), and AML (N = 15). This study uses a Bayesian monitoring approach to guide decision-making using data on the primary efficacy endpoint (ORR) within each tumor-specific cohort. If the data provide high confidence that the true ORR (or rate of CR, incl. CRi/CRp, in AML patients) exceeds a minimal clinically meaningful level, then the results would support continued development (a “Go” decision) for that cohort. If the data suggest that the true ORR is unlikely to meet the desired level of clinical activity, then the results would support a decision to halt further continuation of accrual (a “Stop” decision) for that cohort. Definitions of the decision boundaries can be found in [Section 7.6.6](#). Results that do not meet either the Stop or Go criteria are said to be in the consider zone, where determination of the next course of action will be guided by additional information such as secondary endpoints or external data on similar compounds. This

approach is based on the decision-making framework described in [Lalonde et al, 2007](#) and [Frewer et al, 2016](#).

The minimal clinically meaningful level is defined by the “lower reference value” (LRV), and the desired level of clinical activity is defined by the “target value” (TV). The LRV and TV for each tumor type are determined by medical opinion, evidence from the literature, or data from other compounds developing in the same area. These values are as follows: CRC LRV=10%, TV=20%; OvC LRV=10%, TV=20%; SCLC LRV=30%, TV=40%; TNBC LRV=15%, TV=25%; AML LRV=15%, TV=25%.

Enrollment in a cohort may be stopped for futility prior to reaching the planned sample size if there is a high predicted probability of a Stop decision at the planned sample size. Enrollment in a cohort may be increased by approximately 10 additional patients beyond the planned sample size if the sponsor determines that further data on the primary or secondary endpoints is needed to clarify the efficacy signals for a Go/No-Go decision.

Performance of the study design is evaluated on the basis of the probability of entering each decision zone for given true ORR values at the planned sample size within each cohort. Based on the performance characteristics summarized in [Table 11](#) through [Table 13](#), the sample sizes are adequate to address the study’s objectives.

Table 11 **Statistical Design Performance for CRC or OvC Cohorts of 20 Patients**

	Probability of Making Each Decision for a Given True ORR		
True ORR	Go (%)	Consider (%)	Stop (%)
20% (TV)	59	34	7
15%	35	47	18
10% (LRV)	13	48	39

CRC = colorectal cancer; ORR = overall response rate; OvC = ovarian cancer; LRV = lower reference value; TV = target value

Table 12 Statistical Design Performance for SCLC Cohort of 20 Patients

	Probability of Making Each Decision for a Given True ORR		
True ORR	Go (%)	Consider (%)	Stop (%)
40% (TV)	58	29	13
35%	40	36	25
30% (LRV)	23	36	42

ORR = overall response rate; LRV = lower reference value; SCLC = small cell lung cancer; TV = target value

Table 13 Statistical Design Performance for TNBC and AML Cohorts of 15 Patients

	Probability of Making Each Decision for a Given True ORR		
True ORR	Go (%)	Consider (%)	Stop (%)
25% (TV)	54	38	8
20%	35	48	17
15% (LRV)	18	50	32

AML = acute myeloid leukemia; ORR = overall response rate; LRV = lower reference value; TNBC = triple negative breast cancer; TV = target value

Calculations and simulations to determine decision boundaries and performance characteristics were performed using version 3.3.3 of the R software package (R Core Team).

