complete response (CR; including CR with incomplete recovery of blood counts or platelets [CRi/CRp]).

Hypothesis for the Primary Objectives: Combining galinpepimut-S with pembrolizumab could increase the clinical benefit of pembrolizumab monotherapy ([Seledstov et al, 2015](#); [Kleponis et al, 2015](#)) as assessed by improved ORR values versus historical controls for each individual tumor type tested. This would constitute a “positive efficacy signal” (as relevant to each particular tumor type tested) and warrant broader future clinical investigations. Further, the combination will not increase the burden of toxicities and will have an overall similar/comparable adverse event (AE) profile as pembrolizumab monotherapy.

(N.B.: The a priori statistical assumptions and threshold criteria supporting the definition of a positive signal are described in detail in [Section 7.6](#)).

Secondary Objectives:

- To evaluate the clinical benefit of galinpepimut-S in combination with pembrolizumab in patients with selected advanced cancers through the analysis of time to response (TTR), time to next treatment, and duration of response (DOR)

Hypothesis for the Secondary Objectives: Galinpepimut-S in combination with pembrolizumab could increase the clinical benefit of pembrolizumab monotherapy upon parameters other than ORR, such as TTR, time to next treatment, and DOR. In

case of a positive efficacy signal, such effects could be correlated with effects on ORR (vs. historical controls).

Exploratory Objectives:

- To further characterize the immunogenicity profile of galinpepimut-S when administered in this combination, i.e., its ability to generate WT1-specific immunocyte responses through analyses of WT1-specific CD8 and CD4 cells in PB, as well as WT1-specific memory CD8 T cells, myeloid-derived suppressor cells [MDSC], and T-regulatory cells (Treg) in PB
- To gauge the general immunodynamics effects upon non-antigen-specific lymphocyte immunophenotypic subtypes will be studied in PB via flow cytometry
- To assess the effects of the combination on defined biomarkers of immune checkpoint activity in the tumors (or bone marrow for AML patients) and their surrounding microenvironment (pharmacodynamics specific to pembrolizumab)
- To assess the association between selected biomarker readouts and clinical efficacy measures at specific time-points, using pre-treatment and on-treatment tumor biopsies
- To assess OS and progression-free survival (PFS)

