“consolidation” strategies, such as those including checkpoint inhibitors and TAA-directed immunizing vaccine-type therapies, like galinpepimut-S, either alone or in combination.

The strong expression of WT1 protein in OvC coupled with its proposed mechanism of action makes it a rational target for immunotherapy. WT1 expression is highly prevalent in OvC (Dupont et al, 2004). Indeed, WT1 expression is high enough that pathologists routinely use IHC stains for WT1 with a standardized convention for describing expression and determining as “positive” or “negative” to help distinguish epithelial ovarian cancers from other tumors (Al-Hussaini et al, 2004). WT1 is a particularly sensitive and specific marker for serous ovarian cancer (Acs et al, 2004). Ovarian tissue microarrays at MSKCC (New York, USA) suggest approximately 80% of serous ovarian cancers express WT1 (Lim et al, 2016), thus corroborating earlier studies with IHC (Tornos et al, 2005; Köbel et al, 2009; Karamurzin et al, 2013).

Overexpression of the PD-1 ligand PD-L1 has been demonstrated in OvC and may hinder an effective antitumor immune response (http://abstracts.asco.org/199/AbstView_199_184843.html). The activity of anti-PD1 agents in recurrent OvC in second and third lines of therapy is reflected in ORR values of approximately 15% (Varga et al, 2015; Weiss et al, 2017). In a previous clinical study with pembrolizumab with 15.5 months of follow-up, as well as in a review of the existing recent literature in the use of PD-1 blockers in OvC, pembrolizumab continued to be well tolerated and demonstrated durable antitumor activity in patients with advanced OvC (Mittica et al, 2016). In view of the above, there is good rationale to investigate the combination of galinpepimut-S plus pembrolizumab in OvC.

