1.3.1.2.3. Small Cell Lung Cancer (Second Line)

Treatment options for patients with SCLC who progress on platinum-based chemotherapy are limited. WT1 expression has not been studied in SCLC as extensively as in NSCLC, mainly due to the relative rarity of the former. Nonetheless, WT1 positivity is higher (40 to 83%) in SCLC versus NSCLC (Babiak et al, 2014; Menssen et al, 2000; Oji et al, 2002;

Wang et al, 2013). Therefore, WT1 is an appropriate target for direct TAA-specific immunotherapy approaches, such as galinpepimut-S. Pembrolizumab, an anti-PD-1 monoclonal antibody designed to block the interaction between PD-1 and its ligands PD-L1 and PD-L2, has shown antitumor activity in multiple advanced malignancies, including thoracic tumors such as NSCLC and SCLC (<http://meetinglibrary.asco.org/record/109650/abstract>).

The median PFS and OS following initial chemotherapy in extensive stage small cell lung cancer (ES-SCLC) patients are 2 and 7 months, respectively (Ready, 2015). Maintenance therapy with pembrolizumab did not improve PFS in these patients but favorable OS suggests that some SCLC patients can benefit from maintenance pembrolizumab (Clinical trial information: NCT02359019; http://abstracts.asco.org/199/AbstView_199_183991.html). In patients with PD-L1+ SCLC who have progressed on prior platinum-based therapy, pembrolizumab is generally well tolerated and has promising antitumor activity. Enrollment in the SCLC cohort of KEYNOTE-028 is ongoing (Clinical trial information: NCT02054806). The activity of anti-PD1 agents in SCLC in the second line of therapy is reflected in ORR values of about 33 to 37% (Ott et al, 2016; Hellman et al, 2016; Antonia et al, 2016; Riess et al, 2016). In view of the above, there is good rationale to investigate the combination of galinpepimut-S plus pembrolizumab in SCLC.

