3.1.2. Rationale of Study Design

There is clearly an unmet need for novel and effective therapy to improve responses and prolong disease remission/progression-free intervals already achieved with checkpoint blockade monotherapy (Farkona et al, 2016). The objectives of this proposed clinical study

are: (i). to explore clinical outcomes (safety and potentially promising activity) in tumors using a combination of agents that improve immune-mediated anticancer effects, namely, pembrolizumab and galinpepimut-S, and (ii). to maximize the chances of detecting a clinically meaningful efficacy signal in comparison to historical monotherapy data (with pembrolizumab alone) for further validation in larger, randomized trials.

To meet these objectives, the current design of a Phase 1/2 open-label, non-comparative, multicenter, multi-arm clinical study was chosen, as it has been used successfully in similar studies beforehand ([Menis et al, 2014](#); [Toulmonde et al, 2018](#); [Goldberg et al, 2016](#)), and therefore considered as highly suitable for this trial.

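### A Go is judged only against the LRV, which lies below the cited anti-PD-1 response rate in SCLC, OvC and TNBC, so a Go does not by itself show improvement over historical controls; the consequence is robust only in SCLC

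*Combined protocol and SAP*

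**What the plan says.** The Synopsis (Hypothesis for the Primary Objectives) and Section 2.1 describe a positive efficacy signal as added clinical benefit "as assessed by improved ORR values versus historical controls for each individual tumor type tested". A note in the Synopsis adds: "The a priori statistical assumptions and threshold criteria supporting the definition of a positive signal are described in detail in" Section 7.6. Section 3.1.2 names the comparator when it speaks of detecting a signal "in comparison to historical monotherapy data (with pembrolizumab alone").

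Section 7.4 sets the reference values: "OvC LRV=10%, TV=20%; SCLC LRV=30%, TV=40" per cent, and LRV 15%, TV 25% for both TNBC and AML. On what the LRV is: "The minimal clinically meaningful level is defined by the" LRV. It is not called a historical control rate.

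Under Sections 7.6.1 and 7.6.6 a Go needs a high posterior probability that ORR exceeds the LRV, with a 20% false go risk. The TV enters only the Stop rule. The criteria are non-binding.

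The cited anti-PD-1 activity is in Section 1.3.1.2:
- SCLC: activity "in the second line of therapy is reflected in ORR values of about 33 to 37" per cent.
- OvC: activity in "recurrent OvC in second and third lines of therapy is reflected in ORR values of approximately 15" per cent.
- TNBC: about 18%.
- CRC (MSI-L): 0-5%.
- AML: a CR rate on a checkpoint inhibitor plus HMA thought not to exceed 15%.

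**The concern.** The hypothesis is about beating a historical rate, while the rule said to define success is about beating a minimal meaningful level. The two coincide only if the LRV is at or above the historical rate. In SCLC, OvC and TNBC it is below the rate the protocol itself cites.

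At stake is how a Go will be read. The Synopsis and Section 1.3.1.1 say that meeting the ORR endpoint in a tumor type would warrant a randomized Phase 2 trial. In an uncontrolled, open-label study, a Go could be reported as improvement over pembrolizumab alone when the response rate is no better than the cited one.

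**Working it through.** **Inputs.** N, LRV, TV and Go counts from Section 7.4 and Table 14: SCLC 20, 30%, 40%, Go at 8 or more; OvC 20, 10%, 20%, Go at 4 or more; TNBC 15, 15%, 25%, Go at 4 or more. Jeffreys prior Beta(0.5, 0.5) from Section 7.6.1. Cited rates from Section 1.3.1.2.

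**Formulas.** With x responses in n patients the posterior is Beta(0.5 + x, 0.5 + n − x), and P(ORR > r) = 1 − F(r), F being its distribution function. P(Go | p) is the sum over k ≥ g of C(n,k) p^k (1 − p)^(n − k), with g the Go count.

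**Reproducing the plan.** The Go count is the smallest x with P(ORR > LRV) ≥ 0.80.
- SCLC: 7/20 gives 0.696 and 8/20 gives 0.836, so Go at 8.
- OvC: 3/20 gives 0.786 and 4/20 gives 0.922, so Go at 4.
- TNBC: 3/15 gives 0.726 and 4/15 gives 0.892, so Go at 4.

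P(Go) is 0.228, 0.399 and 0.584 in SCLC at true rates of 30, 35 and 40%, and 0.133, 0.352 and 0.589 in OvC at 10, 15 and 20%. These match Table 14 and Tables 11 and 12. The TV is not needed to obtain any Go count.

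**Against the cited rates, at the minimum Go.**

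| Cohort, count | Posterior | Rate r | P(ORR > r) | Flat prior | P(Go) if true ORR = r |
|---|---|---|---|---|---|
| SCLC 8/20 | Beta(8.5, 12.5) | 33% | 0.752 | 0.770 | 0.327 |
| | | 35% | 0.686 | 0.706 | 0.399 |
| | | 37% | 0.616 | 0.636 | 0.473 |
| OvC 4/20 | Beta(4.5, 16.5) | 15% | 0.749 | 0.803 | 0.352 |
| | | 14% | 0.790 | not needed | 0.304 |
| TNBC 4/15 | Beta(4.5, 11.5) | 18% | 0.814 | not needed | 0.278 |

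The flat prior is Beta(1, 1). In the other two cohorts the minimum Go is comfortably above the cited figure: CRC 4/20 gives 0.993 against 5%, and AML 4/15 gives 0.892 against 15%.

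**Do the planned outputs fill the gap?** At the minimum Go, P(ORR > TV) is 0.506 in SCLC and 0.523 in OvC. The 95% credible intervals are 21-62% and 7-41%, and both contain the cited rates. So these outputs do not answer the historical question at the boundary.

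**Above the minimum.** One more response in OvC (5/20) gives 0.890 against 15%. In SCLC, 9/20 gives 0.872, 0.827 and 0.773 against 33, 35 and 37%, and 10/20 gives 0.885 against 37%. The shortfall is confined to the lowest one or two Go counts.

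**The case against.** The best defence is that the rule does what the objectives ask. The Synopsis and Section 2.1 also frame the aim as deciding whether activity is sufficiently promising for further study, and judging a Go against a minimal meaningful level fits that aim. A Go is non-binding, is weighed with a full medical review, and leads to a randomized trial that could test improvement. The minimum Go is an observed rate (40% in SCLC, 20% in OvC) above the cited figure. Tables 11 and 12 already print P(Go) of 35% at a true 15% and 40% at a true 35%. All of this stands. It limits the point to what a Go may be said to show. It does not remove the Synopsis note that ties the definition of a positive signal to Section 7.6, and the tables do not identify those rows as about the cited rates.

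The benchmark is also soft, and that stands too. The comparator is pembrolizumab alone, but the SCLC text includes a statement on pembrolizumab "In patients with PD-L1+ SCLC who have progressed on prior platinum-based therapy", and the reference titles behind the SCLC and OvC rates include nivolumab with or without ipilimumab, a PD-L1-positive ovarian study and a pembrolizumab-plus-chemotherapy study. The OvC cohort also requires platinum-refractory or -resistant disease. The rates are therefore a range, not constants. That is a reason to fix the range before the data are seen.

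Three stronger readings are tempting and are not supported:
- That the LRVs or Go boundaries are wrong. The LRV is not defined as a historical rate, and TNBC shows that an LRV below the cited rate need not matter.
- That 33-47% of SCLC Gos would be false. Those are probabilities of a Go given no benefit over the cited rate. The chance of no improvement given a Go depends heavily on the prior: against 35% in SCLC, 3% under Jeffreys and 39% with true ORR uniform on 30-40%; against 15% in OvC, 2% and 33% (uniform on 10-20%).
- That the trial will never compare with history. Section 7.6 defers details to a separate SAP that is not reproduced here, so the gap is established only for Section 7.

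**Conclusion.** The mismatch between hypothesis and decision rule is real and should be fixed. It concerns what a Go is said to mean. It is not an arithmetic error, since every Go count and tabulated probability checked above reproduces.

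- SCLC: robust. At the minimum Go the probability of exceeding the cited rate is 62-75% (64-77% with a flat prior), below 80% throughout. If the true rate is the cited one, a Go occurs 33-47% of the time, against 23% in the row labelled LRV.
- OvC: borderline. 75% against 15%, but 79% against 14% and 80% against 15% with a flat prior. P(Go) at 15% is 35%, against 13% at the LRV.
- TNBC: the LRV is below the cited rate, but 4/15 still gives 81%.

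These figures assume the cited rates approximate the monotherapy rate in this population, which the documents do not establish. They use the planned cohort sizes. The 80% yardstick is borrowed from the plan's LRV criterion; the plan sets no such level for historical rates.

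**What to change.** In Sections 7.6.1 and 7.6.6, leaving all boundaries and sample sizes as they are:

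1. Prespecify for each cohort the historical rate, or range, behind the hypothesis, with its source population.
2. Report the posterior probability that ORR (CR/CRi/CRp rate in AML) exceeds that rate or range, beside those for the LRV and TV, including for any expanded cohort.
3. State that a Go means ORR probably exceeds the LRV and supports continued development, and is not in itself evidence of improved ORR over historical controls. Align the Synopsis note with this.
4. Label the 15% row of Table 11 (for OvC) and the 35% row of Table 12 as about the cited anti-PD-1 rates.

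The cost is some wording and one extra posterior probability, or a short range, per cohort.

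A numeric cutoff for calling a result improved is optional and for the sponsor to choose. If 80% were used with the cited rates, the label would need 5/20 in OvC, and 9/20 (33-35%) or 10/20 (37%) in SCLC. The chance of the label with no improvement would be 17% in OvC instead of 35%, and 18, 24 or 17% in SCLC at 33, 35 or 37% instead of 33, 40 or 47%. The price is that at a true ORR equal to the TV the label would be reached only 37% of the time in OvC (Go 59%) and 40% in SCLC, or 24.5% with the 37% benchmark (Go 58%). The other Gos would still support continued development.

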7.5. Analysis Sets

- The full analysis set (FAS) comprises all patients who are assigned to receive study treatment as per the ITT principle, regardless of whether or not they subsequently go on to receive study treatment or whether they deviate from the protocol in any major way.

- The modified intent-to-treat (mITT) set comprises all patients who are assigned to receive study treatment and have at least 1 post-baseline efficacy assessment (RECIST 1.1), even if they deviate from the protocol in any major way. The mITT will also include any patient that goes off study treatment because of clinical progression prior to the first scheduled per-protocol scan.
- The safety analysis set comprises all patients who receive any amount of study drug.
- The per-protocol set (PPS) comprises all patients who are assigned to receive study treatment, receive at least 1 injection of study treatment, have at least 1 post-baseline efficacy assessment (RECIST 1.1), and do not deviate from the protocol in any major way.

All efficacy analyses will be based on the FAS and will be conducted on the mITT set and PPS populations for exploratory purposes. For CRC patients, only those with MSS and MSI-L will be included in the efficacy primary analysis. The safety analyses will be based on the safety analysis set and will group patients according to treatment actually received. Secondary and exploratory efficacy analyses will be performed on the ITT/FAS as well as on the mITT and PPS populations for exploratory purposes.

Major protocol deviations will be defined in more detail in the study statistical analysis plan (SAP), and may include, but not be limited to, incorrect diagnosis and poor compliance.

All analyses using the PPS will group patients according to treatment actually received.

